**Figure 1 - Study Design**

A: ECC 1.7 g BID  
 B: ECC 4.25 g BID  
 D: Day  
 Screening: 15-day duration

The duration of the clinical portion of this study (excluding the screening period) is expected to be approximately 43 days. The actual overall study duration may vary.

The end of the study is defined as completion of the last visit or study procedure, as shown in the schedule of activities) for the trial, globally.

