	
12. Subjects who took an Investigational Product (IP) in the 30 days prior to the first study drug administration
 
13. Any other clinically significant condition that is considered by the principal investigator as being susceptible to put the patient at greater safety risk, influence response to study product, or interfere with study assessments.

Number of Sites and Patients	3 clinical sites and 18 patients
Treatments	
Product: ECC capsules, 425 mg (size 00)
 
In order to fully blind the study, the double dummy technique will be used, i.e. the lowest dose (1.7 g daily) will be co-administered with an ECC matching placebo.
 
Treatment A (“low” dose): 1.7 g total daily dose of ECC, BID + placebo
 
Treatment B (“high” dose): 4.25 g total daily dose of ECC, BID
 
Mode of administration: Oral, capsules taken at least 30 minutes before breakfast and the evening meal
 
Manufacturer: Pharmascience Inc.

Concomitant Medications	
Concomitant antidiarrheal drugs, such as loperamide, are allowed as long as their dose and dosing regimen remain stable at least 2 weeks before and for the total duration of the study.
 
Antacid medications, such as H2 antagonists, and OTC products are prohibited. PPIs are allowed as long as their dose and dosing regimen are stable during the study. IBS-D medications, spasmolytics and any drug exerting significant effects of gastrointestinal transit are also prohibited. Gut trophic factors such as growth hormone and GLP-2 are also prohibited.
 
Standard of Care, concomitant medications are allowed during the study only if judged essential by investigator and with a stable dose and dosing regimen for at least 2 months prior to enrolment and during the study. However, loperamide dose may be modified by the investigator if absolutely necessary. Loperamide doses will be recorded in the patient diary, on a daily basis.

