Administration	
In each of the study periods, patients will be instructed to take two doses of ECC capsules daily (BID regimen), in the morning, at least 30 minutes before breakfast and before evening meal, for 14 days.
 
Patients randomized to Treatment A (Low dose, 1.7 g daily) will take 2 x 425 mg ECC capsules + 3 x placebo capsules in the morning and repeat in the evening.
 
Patients randomized to Treatment B (High dose, 4.25 g daily) will take 5 x 425 mg ECC capsules in the morning and repeat in the evening.
 
Capsules should be taken with water at ambient temperature. The capsules should be swallowed whole and not be chewed or crushed.

Dose Justification	Currently, at least 4 g daily is the dose recommended for regular, non-enteric coated cholestyramine. ECC may be as or more effective at a lower dose, i.e. 1.7 g daily.
Sample Size Justification	Using an alpha of 0.05 and beta of 0.2, a paired t-test, and assuming a standard deviation of 1.265 and a 20% attrition rate; 18 patients are required to show a minimal 25% difference between the two treatments in the reduction of the weekly number of bowel movements after 14 days of treatment (measured during the second week of treatment). Moreover, with 18 patients, we will have more than 80% power to detect a minimal reduction of 4 weekly bowel movements after 14 days of treatment with either 1.7 or 4.25 g of ECC per day (pooled data; assuming SD of 2).
Study Duration	12 - 16 months

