#### 4. GLOSSARY OF TERMS AND ABBREVIATIONS

AE: Adverse Event  
ALT: Alanine Aminotransferase  
AST: Aspartate Aminotransferase  
AUC: Area Under the Curve  
BAD: Bile Acid Diarrhea  
BAM: Bile Acid Malabsorption  
BID: *Bis In Die* (Latin), twice daily  
BM: Bowel Movement  
BMI: Body Mass Index  
BSFS: Bristol Stool Form Scale  
BW: Body Weight  
CBC: Complete Blood Count  
CRF: Case Report Form  
CRO: Contract Research Organization  
CV: Curriculum Vitae  
DDI: Drug-drug Interaction  
EC: Ethics Committee  
ECC: Enteric-coated Cholestyramine  
ECG: Electrocardiogram  
GCP: Good Clinical Practice  
GI: Gastrointestinal  
GLP: Glucagon-like Peptide  
GMP: Good Manufacturing Practice  
HCTZ: Hydrochlorothiazide  
HPN: Home Parenteral Nutrition  
ICF: Informed Consent Form  
IRB: Institutional Review Board  
ITT: Intent-to-Treat  
IV: Intravenous  
IWRS: Interactive Web Response System  
MedDRA: Medical Dictionary for Regulatory Activities  
PK: Pharmacokinetic  
PO: *per os* (Latin), by mouth, orally  
PP: Per Protocol  
PPI: Proton Pump Inhibitors  
QD: *Quaque Die* (Latin), every day/daily  
QTc: QT corrected for heart rate

RBC: Red Blood Cells

SAE: Serious Adverse Event

SAP: Statistical Analysis Plan

SD: Standard Deviation

SUSAR: Suspected Unexpected Serious Adverse Reactions

TEAE: Treatment Emergent Adverse Event

TMF: Trial Master File

TPN: Total Parenteral Nutrition

VAS: Visual Analog Scale

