## 7.2 Study Overview

### 7.2.1 Study Design

This is a multiple center, randomized, double-blind, double dummy, 2-period, 2-sequence cross-over study design (Figure 1). The study will be conducted across three study centers. A total of 18 patients will be selected to participate in the study. All 18 patients will receive treatment with ECC during each study period. Patients will be randomized to either “low” dose ECC (1.7 g with matching placebo BID), or “high” dose ECC (4.25 g BID) daily for 14 days, followed by a 14-day washout, and then allocated to the other treatment for the second period.

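### Does the Figure 1 legend, by attaching BID to each gram amount, put the dose of the two arms in doubt?

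*Combined protocol and SAP*

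**What the plan says.** The Figure 1 legend labels Treatment B "B: ECC 4.25 g BID". The line for Treatment A has the same form with 1.7 g. The glossary entry for BID reads "Latin), twice daily".

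Section 7.2.1, which introduces the figure, uses similar wording: "dose ECC (1.7 g with matching placebo BID" for the low dose and "dose ECC (4.25 g BID) daily for 14 days" for the high dose.

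Elsewhere the same gram amounts are daily totals:

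- **Synopsis, Treatments:** "1.7 g total daily dose of ECC, BID + placebo" for Treatment A and "4.25 g total daily dose of ECC, BID" for Treatment B.
- **Synopsis, Administration:** "Treatment A (Low dose, 1.7 g daily) will take 2 x 425 mg ECC capsules + 3 x placebo capsules in the morning", repeated in the evening, and "Treatment B (High dose, 4.25 g daily) will take 5 x 425 mg ECC capsules in the morning and repeat in the evening".
- **Section 5.7:** 4 capsules a day for the low dose and 10 for the high dose, with the same daily gram amounts.
- **Section 7.3:** the same daily doses, taken BID as 2 or 5 active capsules per intake, with 3 placebo capsules added at each low-dose intake.
- **Section 14.6.1:** the tests of the high and low doses name 4.25 g and 1.7 g daily.

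**The concern.** A gram amount followed directly by BID normally means that amount at each of two intakes. The legend has no word such as daily or total to prevent that reading, although the Synopsis and Section 7.3 both carry such a word. A reader who sees only the figure could therefore take each arm to receive double what the rest of the protocol states.

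The trial's primary objective includes selecting a dose (Section 6.1), so the dose of each arm is a central quantity. If the protocol really left it open, the trial could not say what it had compared, and the conclusion from the high-versus-low test would be attached to an uncertain regimen. That would be serious, so it is worth checking whether the doubt extends beyond the legend.

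**Working it through.** **Inputs**

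- Capsule strength: 425 mg = 0.425 g (Synopsis, Treatments).
- Active capsules per intake: 2 for Treatment A, 5 for Treatment B (Synopsis, Administration; Section 7.3).
- Intakes per day: 2 (same places; glossary entry for BID).
- Capsules per day: 4 and 10 (Section 5.7).
- Legend amounts: 1.7 g and 4.25 g, each followed by BID (Figure 1).

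**Step 1. Reproduce the stated daily amounts.** Daily dose = active capsules per intake × 0.425 g × 2.

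- A: 2 × 0.425 = 0.85 g per intake; × 2 = 1.7 g a day, from 2 × 2 = 4 capsules.
- B: 5 × 0.425 = 2.125 g per intake; × 2 = 4.25 g a day, from 5 × 2 = 10 capsules.

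Both results match the Synopsis and Sections 5.7, 7.3 and 14.6.1 exactly, in grams and, where capsules are given, in capsule counts.

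**Step 2. Read the legend literally.** Daily dose = legend amount × 2.

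- A: 1.7 × 2 = 3.4 g a day, which would need 3.4 / 0.425 = 8 active capsules.
- B: 4.25 × 2 = 8.5 g a day, which would need 8.5 / 0.425 = 20 active capsules.
- Ratio to Step 1: 3.4 / 1.7 = 8.5 / 4.25 = 2.0.

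The protocol nowhere gives 8 or 20 active capsules a day. The factor is exactly 2 in both arms. That is what a dropped qualifier would produce, although the legend itself does not say that this is the cause.

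**Step 3. Ask which parts of the trial depend on the legend.**

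| Function | Where it is set | Form of the dose there |
|---|---|---|
| Definition of A and B | Synopsis (Treatments); Section 7.3 | Daily total, split BID |
| Instructions for intake | Synopsis (Administration); Section 7.3 | Capsules per intake |
| Supply | Sections 10.1 to 10.3 | Numbered kits for one period, assigned through the IWRS |
| Primary tests | Section 14.6.1 | Daily amounts |
| Sample size | Section 14.1 | No gram amount used |

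The sample size inputs are a mean change of 4 bowel movements per week, an SD of 2.0 and a correlation of 0.80. The SD of the difference is √(2.0² + 2.0² − 2 × 0.80 × 2.0 × 2.0) = √1.6 = 1.265, as the plan states. Doubling or halving a gram amount in a figure key alters none of these inputs.

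**Step 4. Place Section 7.2.1.** Its high-dose phrase puts daily straight after the bracket, and in its low-dose phrase BID follows the placebo. Both can be read as a daily amount taken in two parts. The wording is loose, but it does not force the doubled reading. If it is read that way, the mismatch is confined to the two legend lines.

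**The case for a change.** The strongest case for acting is that the contradiction is on the page and nothing in the protocol corrects it. Where the authors mean a divided total, they say so in the Synopsis and in Section 7.3; the legend omits the very word that separates the two readings. Treating it as shorthand means importing the meaning from other sections. A design figure is also often read on its own, dose selection is the point of the trial, and correction would cost only a few words. Nor is this a fault of text extraction, since both legend lines survive complete.

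Most of this stands as a description of the text. The literal reading does double the dose, and the shorthand explanation is an inference that only the sponsor can confirm. What does not follow is any effect on the trial. The legend decodes two letters and is visibly abbreviated: it omits the placebo capsules in Treatment A. Nothing in the documents indicates that dosing, supply or analysis is taken from it. The dose-selection argument also loses force, because the comparison rests on the arms as defined in Section 7.3 and tested in Section 14.6.1, and those two agree. Turning the factor of two into capsules per intake or per period restates the same missing qualifier and adds no evidence of a supply or exposure problem.

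**Conclusion.** This is a clerical inconsistency, and no change to the plan follows. Its size is a factor of exactly 2.0 on a literal reading of two legend lines, with loose but not contradictory wording in Section 7.2.1. The definitions, capsule instructions and primary tests agree with one another, and the sample size, endpoints and analysis are the same whichever way the legend is read.

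The legend and Section 7.2.1 should be reconciled with the Synopsis and Sections 5.7, 7.3 and 14.6.1 when the sponsor next edits the protocol. That is an editorial matter for the sponsor. Restating every dose in one uniform format would be optional.

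The conclusion rests on two conditions. First, dosing and supply follow the capsule-level text and the IWRS kit assignment, as the documents describe. Second, only the legend text could be read; the graphic was not available, so it is unknown whether it carries a qualifier. No position is taken on which dose is right.

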#### 7.2.2. Study/Treatment Arm Stopping Rule Guideline

The following recommendations are proposed for stopping the enrolment and/or further drug administration in a given treatment arm. An agreement will be reached with the Study Medical Monitor and the Sponsor on making such decisions. The following guidelines will be followed:

- Occurrence of any case of death that may be attributed to ECC (in such a case, the blind will have to be broken and allocated treatment dose identified);

- Occurrence of a significant number of unexpected SAEs that could be attributable to the drug (at least *probable* causality relationship) and that raise Investigators/Sponsor concerns about patients' safety;
- Increased frequency and/or severity of expected cholestyramine-related AEs, that in the judgment of the Investigators/Sponsor, will result in the advice to discontinue ECC treatment.

### 7.2.3 Individual Patient Stopping Rules

The following should be used as a guide for the Investigator to determine if the study drug administration is to be interrupted:

- A subject develops a medical condition that requires prolonged concomitant therapy with a prohibited medication or prolonged interruption of the study drug (more than 2 consecutive days)
- Occurrence of an AE or SAE that could be attributable to the drug (at least *probably* causality relationship) or not, and causes discontinuation of study drug for more than 2 days;
- High and unexpected frequency and/or severity of AEs (at least *probably* causality relationship), serious or not, that in the judgment of the Investigator, requires withdrawal of the patient from the study.

### 7.2.4 Treatment Arm Dose Reduction Guideline

No ECC treatment dose reduction will be permitted during the study, within each treatment arm.

## 7.3 Blinding and Randomization

This study will be fully blinded, using the double dummy technique (combination of active ECC capsules and matching placebo in the low dose treatment arm). Subjects will be randomized to one of the following 2 treatments per period (Table 1):

- **Treatment A:** ECC at the 1.7 g daily dose, administered BID as 2 capsules of ECC, plus 3 capsules of placebo, at least 30 minutes before breakfast and 2 capsules of ECC, plus 3 capsules of placebo at least 30 minutes before evening meal.
- **Treatment B:** ECC at the 4.25 g daily dose, administered BID as 5 capsules of ECC at least 30 minutes before breakfast and 5 capsules of ECC at least 30 minutes before evening meal.

The capsules should be swallowed whole and not be chewed or crushed. All 18 patients will receive both ECC doses by the end of the study.

If the patient misses the morning dose, they should take the dose at least 30 minutes before lunch. If the patient misses the evening dose, they should skip that dose. Doses should not be doubled. Patients should note the times that they take the study medication on their bowel movement diaries.

**Table 1 - Randomization**

	Period 1	Period 2
Sequence AB (n=9)	Treatment A	Treatment B

Sequence BA (n=9)	Treatment B	Treatment A
-------------------	-------------	-------------

JSS Medical Research will develop the computer-generated randomization sequences to be programmed into the Interactive Web Response System (IWRS), according to the study design, the number of subjects and the sequence of treatment administration. The IWRS will assign a randomization number to each patient. The random allocation of each sequence of drug administration to each subject is done in such a way that the study is balanced. Once generated, the randomization code will be final and will not be modified.

**7.4 Procedure for Unblinding**

This is a double-blind study. Patients, investigators and site staff, Sponsor and CRO personnel, and data managers will be kept blinded to treatment assignments until the end of the study, except for emergency unblinding as described below.

Only the Packaging/Distribution provider’s unblinded staff and CRO staff administering the IWRS or performing the statistical analyses will be knowledgeable of individual treatment assignments. As well, in the case of emergency unblinding as described below, some additional people will become aware of treatment assignment for specific patient(s).

The study blind may be broken for an individual patient or several patients in the event of an emergency in which knowledge of the treatment assignment is needed for the safety of the patient(s) and/or for medical decision-making or as required by local regulatory authority. Unless the event for which the blind needs breaking is life-threatening, the investigator must first contact the study’s medical monitor (or designee) prior to breaking the blind. The investigator will obtain unblinding information from the staff administering the IWRS. The reason and justification for breaking the blind must be fully documented in the source documentation and captured on the patient(s) electronic case report form (e-CRF).

**8. SELECTION AND WITHDRAWAL OF PATIENTS**

Subjects who meet all the inclusion criteria and none of the exclusion criteria at the screening visit will be eligible for participation in this study. Continued eligibility will be assessed upon baseline visit at start of Period 1, prior to the first study drug administration.

An effort will be made to include similar proportions of males and females in the study.

**8.1 Inclusion Criteria**

1. Adult, ambulatory male and female subjects
2. Provision of signed and dated informed consent form (ICF)
3. Age ≥ 18 years and ≤ 80 years
4. Stable SBS, of:
  - a. Non-surgical origin; OR
  - b. Surgical origin where the last surgical ileal resection was performed at least 6 months prior to enrolment

5. Partial, Home Parenteral Nutrition and/or parenteral fluids are allowed, at a maximum frequency of 6 times a week throughout the trial, as long as the regimen has been stable for at least 2 weeks prior to screening and is expected to remain unchanged during the study
6. At least 50 % of the colon being intact
7. Intact duodenum
8. BMI  $\geq$  18
9. Presence of stable chronic diarrhea for at least 3 months prior to enrolment as evidenced by medical history
10. Presence of stable chronic diarrhea during the 2-week screening diary period before randomization, as evidenced by completion of a screening diary demonstrating:
  - a. Mean daily production of at least 3 soft or watery stools (BSFS scores 6 or 7); **or**
  - b. More than 3 bowel movements per day on average with >25% of them being BSFS type 6 or 7
11. Stated willingness to comply with all study procedures and availability for the duration of the study
12. Clinical laboratory values within the laboratory's stated normal range; if not within this range, they must be without clinical significance, as determined by the investigator
13. Female subject must meet one of the following criteria:
  - a) Participant is of childbearing potential and agrees to use one of the accepted contraceptive regimens from at least 30 days prior to the first study treatment administration through to at least 30 days after the last dose of the study treatment. An acceptable method of contraception includes one of the following:
    - a) Abstinence from heterosexual intercourse
    - b) Systemic contraceptives (combined birth control pills, injectable/implant/insertable hormonal birth control products, transdermal patch)
    - c) Intrauterine device (with or without hormones)
    - d) Condom with spermicide
  - b) Participants of non-childbearing potential, defined as surgically sterile (i.e. has undergone complete hysterectomy or bilateral oophorectomy) or is in a menopausal state (i.e. at least 1 year without menses prior to the first study drug administration) are eligible

## 8.2 Exclusion Criteria

1. Patients with known or suspected intestinal strictures of clinical relevance as judged by the Investigator
2. Active inflammatory bowel disease (IBD) or fistula during the screening period as judged by the Investigator
3. Crohn's disease patients not being in clinical remission for the last 12 weeks prior to randomization
4. Diarrhea caused by other causes than SBS
5. Presence of clinically significant steatorrhea, requiring pancreatic enzymes supplementation
6. Presence of complete biliary obstruction
7. Presence of active cancer (except resected cutaneous basal or squamous cell carcinoma and except *in situ* cervical cancer) and/or the need to receive chemotherapy or radiotherapy during the study
8. History of allergic reaction to cholestyramine or any excipient of the investigational drug product or placebo such as lactose, or packaging components.
9. Females who are lactating at screening

10. Females who are pregnant according to the pregnancy test at screening or prior to the first study treatment administration
11. Significant history (at least 3 consecutive months in the year prior to Screening) of drug dependency or alcohol abuse (> 3 units of alcohol per day, intake of excessive alcohol, acute or chronic)
12. Subjects who took an Investigational Product (IP) in the 30 days prior to the first study drug administration
13. Any other clinically significant condition that is considered by the principal investigator as being susceptible to put the patient at greater safety risk, influence response to study product, or interfere with study assessments.

### 8.3 Informed Consent

Subjects are required to provide written informed consent prior to commencement of any protocol procedure. The consent form can be signed up to 28 days before screening visit. When a suitable subject presents with SBS, the Investigator or designee will explain the nature, purpose, risks and benefits associated with the study to the subject and ensure that the subject is given full and adequate written information. Subjects must be informed that they are free to discontinue from the study at any time. The subject should be given opportunity to ask questions and allowed time to consider the information provided. If the subject agrees to participate in the study, the Informed Consent Form (ICF) must be signed by the subject or his/her legal representative to indicate that the subject understands all aspects of the study. The subject's signed and dated informed consent must be obtained before any study procedures are performed. The Investigator will provide the subject with a copy of the ICF.

### 8.4 Study Withdrawal of Patients

A subject may withdraw from the study at any time at his/her own request without prejudice to further treatment or clinical care. In addition, subjects may be withdrawn at the discretion of the Investigator for safety, behavioral, compliance or administrative reasons. Patients should be withdrawn from the study in the event of any of the following:

1. If a patient does not continue to meet eligibility criteria at baseline, the patient will be withdrawn prior to randomization.
2. Safety issues as described in the Study/Treatment Arm or Individual Patient Stopping Rules.
3. If a patient withdraws consent during the treatment period, and more specifically consent to contribute additional outcome information, the patient shall be withdrawn from the study (although it is recommended that the investigator attempts to perform a Treatment Discontinuation Visit Evaluation). If the patient withdrawing consent to further treatment agrees to contribute additional outcome information, then the regular schedule of visits could be maintained, for safety and relevant outcome measures of efficacy.
4. If a patient is serially and persistently noncompliant with study procedures and/or visit schedules, the investigator or the Sponsor may withdraw the patient from the study.
5. A patient's treatment is unblinded by the Investigator.
6. If a female patient or a female partner of a male patient has a confirmed pregnancy (with the exception of a pregnancy resulting from *in-vitro* fertilization), this should be immediately reported to the Medical Monitor and the Sponsor (within 1 working day of discovery) and the female patient shall be withdrawn. The male patient would continue in the study.

The reason for patient withdrawal from the study will be noted on the e-CRF, reported to the Sponsor, and documented in the clinical study report. The investigator should attempt to follow patients withdrawn after first

dosing until resolution of any AEs, or at least 4 weeks after the last dose of study agent, or until completion of pregnancy. Upon withdrawal, no further dosing should be performed for these patients. Investigators shall make reasonable attempts to contact lost-to-follow-up patients for evaluation.

